13.2. Appendix 2: Schedule of Activities

13.2.1. Protocol Defined Schedule of Events

Procedure	Screening Visit ^a	Maintenance Phase										Extension Phase						Withdrawal	Follow-up Phase		
		Week																			
		Baseline, Day 1	4A	4B ^b	5 ^b	8, 12, 16, 20	24	28, 32, 36, 40	41 ^b	44	48	52	56A	56B ^b	60	64, 72, , 80, 88	68, 76, 84, 92			96	Every 4 Weeks After Week 96
Clinical and Other Assessments																					
Written informed consent	X																				
Eligibility Verification (Inclusion/Exclusion Criteria)	X	X ^c							X ^c												
Randomization		X																			
Demography	X																				
Medical History ^d	X																				
Medication History/ Prior ART history	X																				

Procedure	Screening Visit ^a	Maintenance Phase											Extension Phase						Withdrawal	Follow-up Phase		
		Week																				
		Baseline, Day 1	4A	4B ^b	5 ^b	8, 12, 16, 20	24	28, 32, 36, 40	41 ^b	44	48	52	56A	56B ^b	60	64, 72, 80, 88	68, 76, 84, 92	96			Every 4 Weeks After Week 96	Every 12 Weeks After Week 96
Symptom Directed Physical Exam and Medical Assessment ^e	X	X	X	X	X	X	X	X	X	X	X	X	X	X	X	X	X	X	X	X	X	
Weight, Height and BMI ^f		X								X			X				X				X	
Cardiovascular risk assessment	X	X																				
Vital Signs (BP, HR, Temperature) ^g	X	X								X			X				X				X	
12-lead ECG ^h	X	X pre-dose x3	X							X			X				X				X	
CDC HIV-1 classification	X	X																				
HIV Associated Conditions			X	X	X	X	X	X	X	X	X	X	X	X	X	X	X	X	X	X	X	

Procedure	Screening Visit ^a	Maintenance Phase											Extension Phase						Withdrawal	Follow-up Phase		
		Week																				
		Baseline, Day 1	4A	4B ^b	5 ^b	8, 12, 16, 20	24	28, 32, 36, 40	41 ^b	44	48	52	56A	56B ^b	60	64, 72, 80, 88	68, 76, 84, 92	96			Every 4 Weeks After Week 96	Every 12 Weeks After Week 96
CD4+ cell count	X	X		X		X	X	X		X	X	X		X	X	X		X		X	X	X
CD8+ cell count		X		X		X				X			X				X				X	
Urinalysis ^m		X	X			X				X		X					X				X	
Fasting Lab Assessments: Glucose, Cholesterol (Total, HDL and LDL) and Triglycerides ⁿ		X								X							X				X ^o	
Hepatitis B (HBsAg), Anti-HBc, and Anti-HBsAG, Hepatitis C (anti-HCV Ab)	X																					
HLA-B*5701	X																					
PT/PTT/INR	X	X																				

Procedure	Screening Visit ^a	Maintenance Phase										Extension Phase						Withdrawal	Follow-up Phase			
		Week																				
		Baseline, Day 1	4A	4B ^b	5 ^b	8, 12, 16, 20	24	28, 32, 36, 40	41 ^b	44	48	52	56A	56B ^b	60	64, 72, 80, 88	68, 76, 84, 92			96	Every 4 Weeks After Week 96	Every 12 Weeks After Week 96
Renal, bone, marker analytes (blood/urine) ^p	X									X								X			X	
PBMCs ^q	X																	X			X	
Genetics sample ^r	X																					
Pharmacokinetics – CAB + RPV only																						
PK sampling ^s (S)=Storage only				X	X	X	X	X	X	X	X		X	X	S		X				X	S
Investigational Products																						
Oral CAB and Oral RPV Dispensation ^t	X	X									X	X										
IP accountability (Pill Counts)		X	X									X	X									

Procedure	Screening Visit ^a	Maintenance Phase										Extension Phase								Withdrawal	Follow-up Phase
		Baseline, Day 1	Week																		
			4A	4B ^b	5 ^b	8, 12, 16, 20	24	28, 32, 36, 40	41 ^b	44	48	52	56A	56B ^b	60	64, 72, 80, 88	68, 76, 84, 92	96	Every 4 Weeks After Week 96		
IM treatment administration ^u			X		X	X	X		X	X	X	X	X	X	X	X	X	X	X		
Patient Reported Outcomes^v																					
HAT-QoL (short-form)		X				X				X								X			X
SF-12		X				X				X								X			X
HIV TSQs		X		X		X				X								X			X
HIV TSQc ^w										X											X
ACCEPT		X				X				X								X			X
Reason for Switch ^x		X									X										
Preference ^y										X								X			

Procedure	Screening Visit ^a	Maintenance Phase											Extension Phase						Withdrawal	Follow-up Phase				
		Week																						
		Baseline, Day 1	4A	4B ^b	5 ^b	8, 12, 16, 20	24	28, 32, 36, 40	41 ^b	44	48	52	56A	56B ^b	60	64, 72, 80, 88	68, 76, 84, 92	96			Every 4 Weeks After Week 96	Every 12 Weeks After Week 96		
NRS ^z			X	X			X Wk40 only	X									X							
PIN				X				X		X							X						X	

Follow Up Visit: Conduct approximately 4 weeks after the last dose of IP. Required only if the participant has ongoing AEs or lab abnormalities at the last on-study visit. This visit may be conducted by telephone.

- a. Complete all Screening assessments within 35 days. Participants may begin the Maintenance Phase as soon as all Screening assessments are complete. Participants may be rescreened once and will be assigned a new participant number.
- b. Visits at Weeks 4b, 5, 41, and 56b are only for participants randomized to CAB LA + RPV LA or transitioning from current ART to CAB LA + RPV LA during the Maintenance or Extension Phase, respectively.
- c. Confirmation of eligibility to enter the Maintenance Phase, and eligibility to enter the Extension Phase.
- d. Collect full routine medical history plus (report at Baseline visit): HIV risk factors (may be collected at a later study visit), cardiovascular risk factors (assessments include smoking status and history, family history of cardiac events), recent [≤6 months] illicit drug use, intravenous drug use, gastrointestinal disease, metabolic, psychiatric, renal, bone, and neurologic disorders.
- e. Physical exams should be conducted as part of normal routine clinical care but data will not be collected in the eCRF. Medical assessments include any decisions the study staff must make for participants management and/or care of participant.
- f. Height collected at Baseline only.
- g. Measure vital signs after about 5 minutes of rest in a semi-supine position.
- h. A 12-lead ECG will be performed after resting in a semi-supine position for at least 5 minutes. ECGs will be performed pre-dose. ECG will be performed in triplicate at Baseline (Day 1). In addition to a pre-dose ECG, a 2-hour post-dose ECG will be performed at Weeks 4B and Week 48 for subjects randomized to CAB LA + RPV LA only.
- i. Only SAEs related to study participation or to a concomitantly administered ViiV/GSK product will be collected between obtaining informed consent and administration of study drug at Day 1.

- j. On Day 1, the eC-SSRS is to be administered prior to randomization. The eC-SSRS will be administered at each Q4W injection visit through the Week 48 primary endpoint, followed by Q12W thereafter through Week 96 (Week 60, 72, 84, 96). The eC-SSRS will preferably be completed at the beginning of the visit following administration of other PROs required prior to injections.
- k. Women of childbearing potential only. SR=serum, UR=urine. Pregnancy events will be captured starting at Day 1 following exposure to study drug. Serum pregnancy test can substitute for urine pregnancy test if locally required but must be appropriately timed to confirm pregnancy status prior to randomization and first IM administration.
- l. HIV-1 RNA will not be collected for analysis at Week 52 and Week 100 (Week 48 or Week 96 retest will be captured as unscheduled visit). Plasma for storage will be collected at Week 52 and Week 100. Plasma for storage samples will be used for possible future analyses
- m. A morning specimen is preferred. To assess biomarkers: urine albumin/creatinine ratio; urine protein/creatinine ratio; and urine phosphate.
- n. An overnight fast is preferred; however, a minimum of a 6-hour fast is acceptable.
- o. Only collect if the Withdrawal visit occurs at Week 48, or 96.
- p. Blood sample for renal and bone biomarker assessments: **Renal:** Cystatin C; Retinol Binding Protein (RBP); **Bone:** bone specific alkaline phosphatase, procollagen type 1-N-propeptide, type 1 collagen cross-linked C-telopeptide, osteocalcin, 25 hydroxy-Vitamin D
- q. Whole blood/PBMC collection samples may be used for virologic analyses. PBMCs will be collected at Day 1, Week 96, and Withdrawal if prior to Week 96.
- r. Informed consent for genetic research must be obtained before sample collection
- s. One blood sample for CAB and RPV each to be collected at each PK timepoint. PK samples are to be collected pre-dose during visits requiring IM administration. 2-hour post dose samples also taken at Weeks 4b, 48, 56b, and 96. Pre-dose samples at Weeks 56b, 60, and 2 hour post-dose sample at Week 56b are only for subjects transitioning from Current Art arm to CAB LA + RPB LA. Pre-dose samples are to be collected after review of PK diary at Week 4b and 56b and prior to the final oral dose of CAB + RPV. Additionally, PK samples will be taken during the 1-week post-dose Week 5 and 41 visits. PK window allowed for sample collection; includes 3 to 10 days for 1-week post dose sample (Visits 5 and 41); ±one hour for 2-hour post dose sample (Weeks 4b, 48, 56b, and 96).
- t. Only for Participants entering CAB LA+ RPV LA Oral Treatment
- u. Participants switching to CAB LA + RPV LA will take final dose of oral lead-in regimen in the clinic at The Week 4b visit or Week 56b and begin injections. If possible, injections should be spaced approximately 2 cm from one another and from the site of any previous injection and or any injection site reaction. Bring RPV LA to approximately room temperature prior to injecting. Time and location of injection (right or left) as well as needle length used will be collected in the eCRF. The first injection can be performed as soon as central lab results become available and safety parameters are reviewed.
- v. With the exception of the NRS, all Patient Report Questionnaires/Surveys are recommended to be administered at the beginning of the visit before any other assessments are conducted and prior to administration of the NRS is to be given post injection. Conduct questionnaires/surveys at Withdrawal if occurring prior to Week 96.
- w. HIV TSQ (c) to be administered at Week 48 to LA injection arm only
- x. "Reason for switch" will be administered prior to randomization at Day 1. At Week 52, "Reason for Switch" will be given only to participants randomized to the "Current ART" arm.
- y. Preference" question to be administered at Week 48 to patients randomized to CAB LA + RPV LA arm, and at Week 96 to patients randomized to the "current ART arm" who switched to CAB LA + RPV LA at the end of maintenance phase.
- z. NRS will be administered on injection visits approximately 30-60 minutes following injections. Participant should record the maximum level of pain experienced with the most recent injections.

Note: BP – Blood pressure, HR – Heart Rate, HDL – High Density Lipoprotein, LDL – Low Density Lipoprotein, PT Prothrombin Time, PTT Partial Thromboplastin Time, INR International normalized ratio

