13.3. Appendix 3: Assessment Windows

13.3.1. Definitions of Assessment Windows for Analyses

Laboratory data, vital signs, ECGs, health outcomes assessments, and genotypic/phenotypic data will be assigned to assessment windows according to actual dates rather than the nominal visit labels as recorded on the eCRF or in the laboratory database.

In most cases the window around an assessment will include all dates from the midpoints between the target day and that of the previous and the proceeding visits. In general, the nominal target study day for week w is $(7*w) + 1$.

For parameters which are not scheduled to be assessed at particular visits, the all-inclusive assessment windows will still be used; however, data summaries will only report scheduled visits. Assessments at unscheduled visits will be included for ‘any time On-treatment’ time points and in data listings, as well any algorithms that make use of additional data (e.g., Snapshot).

Prior to visit slotting, assessments are first assigned to a study phase (screening, maintenance, extension, or Long Term Follow Up) based on the Tables in Section 13.4.1 and treatment state based on Section 13.4.2.

Maintenance phase assessments are assigned based on the Maintenance Phase Study Day as shown in Table 9. The analysis visits from Week 4 to Week 52 should be only applied to the assessments that are already assigned to Maintenance phase (on-treatment). Extension phase assessments are assigned based on the Maintenance Phase Study day for subjects continuing Q4W IM dosing into the Extension Phase, and based on the Extension Phase Study Day for subjects switching from the control arm to Q4W IM dosing for the Extension phase as shown in Table 10. The analysis visits from Week 56 (except for Follow-up) in the Extension phase should be only applied to the assessments that are already assigned to Extension phase (on-treatment).

Long-term Follow-up phase assessments are assigned based on the LTFU study day as shown in Table 12. The analysis visits in LTFU should be only applied to the assessments that are already assigned to LTFU phase regardless of treatment state. See Section 13.6.1, for derivation of Maintenance, Extension and LTFU Study Day.

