13.3.2. Definitions of Assessment Windows for Data Other than Health Outcome and PK

Table 9 Assessment Windows for Screening & Maintenance Phase Data

Parameters[d] collected in sparse visit [c]	Analysis Window	Target Study Day	Analysis Timepoint
	Study Day ≤ 1 (the first record if there are multiple values)	The day of earliest record	Screening
	Last available recorded value up to and	1	Baseline

Parameters[d] collected in sparse visit [c]	Analysis Window	Target Study Day	Analysis Timepoint
	including the date of first maintenance phase dose of IP		
ECG, CD8, CD4/CD8 ratio	2 ≤ Study Day ≤ 70	29	Week 4
	2 ≤ Study Day ≤ 42		
	43 ≤ Study Day ≤ 70	57	Week 8
	71 ≤ Study Day ≤ 98	85	Week 12
	99 ≤ Study Day ≤ 126	113	Week 16
	127 ≤ Study Day ≤ 154	141	Week 20
urinalysis, CD8, CD4/CD8 ratio	155 ≤ Study Day ≤ 210	169	Week 24
	155 ≤ Study Day ≤ 182		
	183 ≤ Study Day ≤ 210	197	Week 28
	211 ≤ Study Day ≤ 238	225	Week 32
	239 ≤ Study Day ≤ 266	253	Week 36
	267 ≤ Study Day ≤ 294	281	Week 40
	295 ≤ Study Day ≤ 322	309	Week 44
	ECG, CD8, CD4/CD8 ratio, urinalysis, lipids, bone and renal markers	323 ≤ Study Day ≤ 378	337
323 ≤ Study Day ≤ 350			
	For 'Current ART' arm; 351 ≤ Study Day ≤ Maintenance Current ART Stop Day ^[b] + 1 For 'Q4W' arm: 351 ≤ Study Day ≤ Max (Day of Last Q4W IM Dose + 35, Last Oral dose Day + 1) ^[a]	365	Week 52
	For subjects who discontinued from oral lead-in during Maintenance phase, Study Day > (Day of last oral lead-in dose+1) Subjects discontinued from Current ART and not continuing into extension phase Study Day > (Maintenance Current ART Stop Day ^[b] + 1)		Follow-up

[a] Last Q4W IM / last oral dose is only applied to subjects who permanently discontinue from study treatment

[b] Current ART stop day: the last permanently stop day among all ARTs taken during Maintenance phase.

[c] For parameters with sparse collection, post baseline data will only be slotted to those specific analysis windows. The Screening or Baseline slotting will be based on the same rules as all other lab parameters use.

[d] **Urinalysis:** Urine Albumin/Creatinine, Urine Creatinine, Urine pH, Urine Protein/Creatinine, Urine Erythrocytes, Urine Specific Gravity, Urine Leukocytes, Urine Retinol Binding Protein, Urine Phosphate, Urine Creatinine

Bone marker: Bone Specific Alkaline Phosphatase, Osteocalcin, Procollagen 1 N-Terminal Propeptide, Vitamin D, Type I C-Telopeptides

Renal marker: Cystatin C, Retinol Binding Protein

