13.3.6. Multiple assessments within an Analysis Window

If after window assignment there are multiple valid assessments of a parameter within the same window, then the following hierarchy will be used to determine the value to be used for summary statistics of observed values:

For data other than health outcome/PK concentration

1. the assessment closest to the window target Study Day;
2. if there are multiple assessments equidistant from the target Study Day, then the mean of these values will be used. For HIV-1 RNA, the geometric mean of the number of copies will be used as opposed to the arithmetic mean.

For Health outcome (excluding NRS) and PK concentration data,

1. If there are multiple assessments assigned to the same analysis visit, the assessment from the planned nominal visit will be used for summary statistics.

For NRS questionnaire assessments:

1. the assessment closest to the window target date will be used;
2. if there are multiple assessments equidistant from the target date, then the earliest assessment will be used.

Assessments not chosen for use in summary statistics by this algorithm will still appear in the associated listings. Also, such valid assessments will be used when determining values of potential clinical concern for the ‘any time On-treatment’ time point, and for any algorithm that has specific rules for which observation to use (e.g., snapshot algorithm or LOCF)

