13.6. Appendix 6: Derived and Transformed Data

13.6.1. General

Multiple Measurements at One Time Point

- If after window assignment there are multiple valid assessments of a parameter within the same window, then the following hierarchy will be used to determine the value to be used for summary statistics of observed values:
 - the assessment closest to the window target Study Day;
 - if there are multiple assessments equidistant from the target Study Day, then for continuous variables the mean of these values will be used and for categorical variables the worse assessment. For HIV-1 RNA, the geometric mean of the number of copies will be used as opposed to the arithmetic mean
- Assessments not chosen for use in summary statistics by this algorithm will still appear in the associated listings. Also, such valid assessments will be used when determining values of potential clinical concern for the 'any time On-treatment' time point, and for any algorithm that has specific rules for which observation to use (e.g., Snapshot).

Treatment Start Date

Treatment start date is defined as follows:
 
Maintenance Phase
 
 • For subjects randomised to Q4W IM, treatment start date is the date of oral lead-in of CAB+RPV entered onto the IP exposure CRF form when study treatment started. • For subjects randomised to Current ART, treatment start date is the date of the Day 1 visit. 
Extension Phase
 
 • For subjects randomised to Q4W IM, treatment start date is the date of Nominal Week 52 injection date. • For subjects randomised to Current ART, treatment start date is the start date of oral lead-in of CAB+RPV at Extension phase.
Study Day

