3.84.	Safety (Q4W arm only)	liver10/Shell TS12	Summary of Subjects Meeting Hepatobiliary Abnormality Criteria - Post-Baseline– Oral Lead-in Period at Maintenance Phase	(for Q4W arm only)	WK48

Safety Tables (Displays will be for both treatment arms, unless specified)					
No.	Population	IDSL / TST ID / Example Shell	Title	Programming Notes	Deliverable [Priority]
ECG					
3.85.	Safety	EG1	Summary of ECG Findings (Maintenance Phase)		WK48
3.86.	Safety	EG1	Summary of ECG Findings (Maintenance +Extension Phase)	(for Q4W arm only)	WK96, EOS
3.87.	ESP	EG1	Summary of ECG Findings (Extension Phase)	(for Current ART arm only)	WK96, EOS
3.88.	Safety	EG2	Summary of Change from Baseline in ECG values by Visit at Maintenance Phase		WK48
3.89.	Safety	EG2	Summary of Change from Baseline in ECG values by Visit at Maintenance + Extension Phase		WK96, EOS
3.90.	ESP	EG2	Summary of Change from Baseline in ECG values by Visit at Extension Phase		WK96, EOS
3.91.	Safety	EG10	Summary of QTc Values by Category at Maintenance Phase	Mid200056/wk48idsl/Table 8.1043	WK48
3.92.	Safety	EG10	Summary of QTc Values by Category at Maintenance+ Extension Phase	Mid200056/wk48idsl/Table 8.1043 (for Q4W arm only)	WK96, EOS
3.93.	ESP	EG10	Summary of QTc Values by Category at Extension Phase	Mid200056/wk48idsl/Table 8.1043 (for Current ART arm only)	WK96, EOS
3.94.	Safety	EG2	Summary of Change from Baseline QTc Values by Category at Maintenance Phase	Mid200056/wk48idsl/Table 8.1044	WK48
3.95.	Safety	EG2	Summary of Change from Baseline QTc Values by Category at Maintenance+Extension Phase	Mid200056/wk48idsl/Table 8.1044 (for Q4W arm only)	WK96, EOS
3.96.	ESP	EG2	Summary of Change from Baseline QTc Values by Category at Extension Phase	Mid200056/wk48idsl/Table 8.1044(for Current ART arm only)	WK96, EOS
eC-SSR and Others					
3.97.	Safety	VS1	Summary of Change from Baseline in Vital Signs by Visit at Maintenance Phase	CS Core	WK48

Safety Tables (Displays will be for both treatment arms, unless specified)					
No.	Population	IDSL / TST ID / Example Shell	Title	Programming Notes	Deliverable [Priority]
3.99.	Safety	Shell TS14	Summary of Subjects with Post Baseline eC-SSRS Suicidal Ideation or Behaviour at Maintenance Phase		WK48
3.100.	Safety	Shell TS14.1	Summary of Post Baseline Depression and Suicidal and Self-Injury Adverse Events by System Organ Class, Maximum DAIDS Toxicity Grade, and Prior History of Depression, Anxiety and Suicidal and Self-Injury – Maintenance phase		WK48

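### The SAP has no rule separating the CAB arm's 2-hour post-dose ECGs from pre-dose ECGs: by-visit QTc is left ambiguous, and maximum post-baseline QTc draws on more scheduled readings in that arm

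*SAP*

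**What the plan says.** - **Schedule (SAP 13.2.1, footnotes b and h).** ECGs are taken pre-dose, with a triplicate at Day 1. In addition, "a 2-hour post-dose ECG will be performed at Weeks 4B and Week 48 for subjects randomized to CAB LA + RPV LA only". The Week 4B visit itself exists in the Maintenance Phase only for the CAB LA + RPV LA arm (the CAB arm below).
- **Windowing (13.3.1).** "Laboratory data, vital signs, ECGs, health outcomes assessments, and genotypic/phenotypic data will be assigned to assessment windows according to actual dates". Table 9 gives ECGs two post-baseline Maintenance windows: Week 4 (Days 2 to 70, target Day 29) and Week 48 (Days 323 to 378, target Day 337). Neither is split by time relative to dose.
- **Ties.** In 13.3.6 the reading closest to the target day is used, and "if there are multiple assessments equidistant from the target Study Day, then the mean of these values will be used". Section 13.6.1 restates this as "for continuous variables the mean of these values will be used and for categorical variables the worse assessment". Both sections keep unselected readings for any-time on-treatment values of potential clinical concern.
- **Displays.** Table 5 marks QTc under absolute value, change from baseline and maximum post-baseline. In 13.13.7, safety tables cover both arms unless stated otherwise. Tables 3.88, 3.91 ("Summary of QTc Values by Category at Maintenance Phase") and 3.94 carry no pre-dose restriction.
- **Thresholds (8.3).** ECG values of potential clinical interest are a QTc above 450 ms or a change from baseline above 30 ms.
- **General default (13.5.2).** Summaries use planned time in relation to dosing, unless another section says otherwise.

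**The concern.** One arm has a kind of ECG that the other never has, and the rules that feed the two-arm QTc tables do not mention it. Two problems can follow, in opposite directions.

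First, a pre-dose and a 2-hour ECG on the same day are always equally far from the target day, so the tie rule would average them. The CAB by-visit value would then mix two dosing states, while the Current ART value is a single reading. Any effect confined to the post-dose reading would be diluted in that table.

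Second, a maximum over more readings is larger by chance alone. The maximum post-baseline QTc and any-time summaries would show more CAB participants over a threshold even if the drug did nothing to QTc.

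A reader of the QTc tables could therefore see too little in one display and too much in another, without being told why.

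**Working it through.** The SAP states no figure on this point, so there is none to reproduce. The check has three parts.

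**1. By-visit value.** Take a CAB participant whose Week 48 ECGs, pre-dose and 2 hours post-dose, fall on the same day, with no other ECG closer to Day 337. Both readings fall in the Week 48 window and are equidistant from the target. Under 13.3.6 the value used is (pre + post)/2. If the drug adds d ms at 2 hours and nothing pre-dose, the table shows (0 + d)/2 = d/2: 5 ms when d = 10, and 2.5 ms when d = 5. The same applies to the Week 4B pair in the Week 4 window if that pair is closest to Day 29. Under the 13.5.2 default, the two readings would instead be shown separately and nothing is diluted. The SAP does not say which rule governs.

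**2. Number of readings behind a maximum.** The two 2-hour ECGs are extra readings in the CAB arm under either rule. For illustration, take 2 scheduled post-baseline ECGs in Current ART (one in each ECG window) and 4 in CAB (pre- and post-dose at Weeks 4B and 48). If each reading independently has probability p of crossing a threshold, the chance of at least one crossing in k readings is 1 − (1 − p)^k:

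| p | k = 2 | k = 4 |
|---|---|---|
| 1% | 1.99% | 3.94% |
| 2% | 3.96% | 7.76% |
| 5% | 9.75% | 18.55% |
| 10% | 19.0% | 34.4% |

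**3. Allowing for correlation.** This is a simulation of 1,000,000 participants per case with no drug effect. The baseline is the mean of three readings. The post-baseline maximum is taken over 2 readings on separate days, or over 4 readings as two same-day pairs. The within-subject SD and the same-day correlation are assumed. The share with a maximum change above 30 ms is:

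| SD (ms) | Same-day correlation | 2 ECGs | 4 ECGs | Ratio |
|---|---|---|---|---|
| 10 | 0 | 0.942% | 1.821% | 1.93 |
| 10 | 0.5 | 0.922% | 1.684% | 1.83 |
| 10 | 0.8 | 0.903% | 1.427% | 1.58 |
| 15 | 0 | 7.852% | 14.246% | 1.81 |
| 15 | 0.5 | 7.837% | 12.884% | 1.64 |
| 15 | 0.8 | 7.951% | 11.309% | 1.42 |

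The 2-ECG column varies with correlation only through simulation error. A second model (300,000 participants per case) puts half the within-subject variance between days and takes the three baseline readings on one day. It gives higher absolute rates but similar ratios: 1.87% versus 3.26% at SD 10 (ratio 1.74), 4.84% versus 7.98% at SD 12 (1.65), and 10.76% versus 16.48% at SD 15 (1.53).

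With matched pre-dose ECGs, both arms have the same number of readings. At p = 2%, for example, the chance is 3.96% in each arm, instead of 3.96% against 7.76%.

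**The case against.** The strongest reply concerns the averaging. Section 13.3.1 replaces nominal visit labels with dates in order to decide which visit a reading belongs to. It does not address time relative to dose within a visit. Section 13.5.2 can therefore sit alongside it: slot by date, then show pre-dose and 2-hour readings separately. The restated tie rule in 13.6.1 also comes under a heading about multiple measurements at a single time point, and these are two planned time points. This stands as a plausible reading. A reader might infer that the Week 48 CAB value is certainly a pre/post-dose mean, but the SAP never says so. The inference comes from the absence of an exception.

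A reader might also infer that the 2-hour signal is lost. It is not: Table 6 and Figures 5.11 and 5.12 plot individual 2-hour QTc change against 2-hour concentration at Weeks 4B and 48, undiluted.

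Nor do the documents support an exact count such as four or five ECGs against two. The ECG row of the schedule is broken in the extracted text, so it cannot be confirmed whether CAB has a Week 4A ECG or whether Current ART has one at Week 4. The cut-offs used in Tables 3.91 and 3.94, and whether those tables contain maximum rows, are not shown either. The mock shells are not in the document, and the thresholds in 8.3 define values of interest, not table categories.

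Finally, a worst-value safety table that includes every on-treatment reading errs towards finding harm in the investigational arm, which is a reasonable purpose. That is a good reason to keep such a table, but it does not make the table a like-for-like comparison of the arms.

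**Conclusion.** The point holds in two parts of different certainty.

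- **By-visit QTc:** the date-based windows with the tie rule, and the planned-time default, lead to different values for the same participant. The literal windowing rules give a pre/post-dose mean and would halve a purely post-dose effect in that table. This is a conflict to reconcile, not an established error.
- **Maximum and any-time QTc:** under either reading, the CAB arm contributes at least two more scheduled ECGs per participant who attends both visits. Ascertainment alone raises its share over a threshold by about 1.4- to 2-fold. That figure rests on 4 against 2 readings, no drug effect, and assumed within-subject SDs of 10 to 15 ms. The ratio is steadier than the absolute rates, which run from about 1% to 16% across the assumptions tried.

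No formal QTc test is planned and the displays are descriptive. The consequence is therefore misleading safety tables, not a wrong confirmatory conclusion. It is still worth correcting, because the remedy uses data already collected.

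**What to change.** 1. In 13.3 (Table 9 and 13.3.6) and 13.6.1, state that planned time, pre-dose or 2 hours post-dose, is kept as a separate time point for ECGs and that the tie rule does not average across it. Cross-refer to 13.5.2 so that the sections agree.
2. Base the two-arm by-visit QTc tables, and a matched maximum and category comparison, on pre-dose ECGs at visits scheduled in both arms.
3. Add a summary of the 2-hour ECGs at Weeks 4B and 48 for the CAB arm only.
4. Keep the any-time maximum over all on-treatment ECGs, including post-dose and unscheduled readings, as a safety display. Footnote it with the number of ECGs per arm.

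The cost is SAP and programming wording plus one or two extra displays. No new data are needed, and no reading is dropped from the safety maximum.
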